## Specific Aims

Hispanic women (Latinas) experience mental and emotional health (MEH) concerns and disorders that often go unrecognized by health providers, and even when recognized, Latinas have low-levels of treatment follow-through with biomedical modalities. Using a novel community-directed, solution-based approach to increase access to existing services and nurture culturally meaningful social relationships, it is possible to address social determinants of health and reduce these disparities.

The **goal** of this study is to implement such an approach conceptualized by a community health worker (CHW) to pilot an innovative, multi-level intervention to address social and structural determinants that negatively influence MEH disparities for Latinas from low-income households. The proposed research integrates CHW navigation with group peer support. Both of these strategies have been shown to be culturally appropriate and effective for improving a variety of health outcomes with this population. Our transdisciplinary, community-engaged team will use a convergent parallel mixed method research design to assess the feasibility of the intervention and its impact on six domains of interest: 1) emotional support, 2) informational support, 3) depression, 4) social isolation, 5) empowerment, and 6) social determinants needs. As part of our preparation for future extramural funding, we will include development of an advocacy plan for multi-level social change impact.

**Aim 1. Create a group navigation model to improve mental and emotional health equity for Spanish-speaking Latina women.** In a series of peer group sessions facilitated by [name], a CHW who designed the model, we will create a culturally-appropriate, non-stigmatizing group intervention. The group process will allow participants to explore their own MEH, better understand the ways that mental health influences well-being and everyday dynamics of their lives, and to develop empowering knowledge and action plans through the support of other women. We will document group discussions, processes, and themes, gather information about women's explanatory models of MEH, and administer a multidimensional survey to capture information about the domains of interest. Through individual case management, [name] will work individually with women from the groups to identify their specific social and structural determinants needs, assist them to make an individual action plan, provide them with information about available resources, and help them navigate systems and access resources and services. We will document participant needs and navigation outcomes. **Hypotheses:** Participation will decrease depression, social isolation, and social determinants needs, and increase emotional support, informational support, and women's sense of empowerment.

**Aim 2. Create an advocacy plan.** With data gathered in group meetings and individual navigation sessions, we will identify social and structural barriers that negatively influence participants' MEH outcomes and ability to access resources and services. We will create an advocacy plan to address structural and policy barriers that can be implemented by CHWs and advocacy groups in the future. **Hypotheses:** We can identify factors that negatively influence the MEH and well-being of Latinas. We hypothesize that in the future, we can use this knowledge to develop a strategic plan with the potential to address socio-structural and policy barriers through advocacy.

**Aim 3. Assess the feasibility of the intervention.** We will track recruitment, attrition, attendance at group sessions, and attendance at individual CHW navigation meetings. We will gather survey data and qualitative data to document participant experiences with and perceptions of the group process, working with the CHW, and the value of the intervention. **Hypotheses:** The intervention we pilot will be feasible, acceptable, valuable, and culturally appropriate.

**Expected Outcome.** This pilot study will use team science to test an intervention that emerged organically in the community and contribute to building the next generation of health disparities research using knowledge generated through solution-based investigation as the foundation for submitting an NIH R21 research proposal.

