### **Approach**

Theoretical Model: The model in the study is informed by **socioecological approaches** to address disparities and affect change at **multiple levels** as broadly constructed by a **social and structural determinants of health framework.** We included attention to change at the level of the individual, the social group, and external infrastructure (e.g. political, legal, economic and other social/institutional factors). Our pilot addressed social and structural determinants at each of these levels.

Research Design: We use a **convergent parallel mixed method research design** to implement an intervention to affect **six domains of interest** in the lives of Latinas: 1) emotional support, 2) informational support, 3) depression, 4) social isolation, 5) empowerment, and 6) social determinants needs. Further, we will assess the feasibility of implementing this model with 30 participants. The intervention integrated navigation assistance and case management by a CHW with a peer support group. We gathered both qualitative and quantitative data using a variety of instruments and methods as described below, and we will integrate different types of data during analysis and interpretation.

Team Expertise & Roles: Our transdisciplinary team integrated expertise from anthropology, community-engaged research, social work, counseling, community navigation, and biostatistics, and we are well situated to conduct the proposed research. **[name] [name], the PI**, is a cultural anthropologist and Research Assistant Professor of Pediatrics in the Prevention Research Center. She has over 20 years’ experience conducting community-engaged research with migrants and other marginalized people to improve health and well-being. **[name], Principal Community Mentor and Co-Investigator**, was trained as a Special Education teacher in Aguascalientes, Mexico and

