**Population:** This project involved Spanish-speaking Latinas from low-income households. Participants was recruited from the International District and South Valley neighborhoods of Albuquerque and screened for language, self-reported ethnic identity as Latino/Hispanic, and self-reported income below 250% of the Federal Poverty Level. The majority of the participants were Mexican immigrants with one participant who was from Central America and one who was a second generation Mexican immigrant.

**Recruitment:** During month #2 prior to the start of the intervention, [name] recruited 30 participants through the Pathways Program, the Simplemente Salud Clinic and Centro Sávila. In the course of regular meetings with clients who request a range of services, she identified identify and invite those who might benefit from the proposed model. While participants experessed interest int eh program, lower numbers than anticipated joined the study from the first 3 cohort. We therefore changed the implementation strategy to allow for two sequential cohorts, one in the Fall and and one in the Spring.

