#### Intervention Implementation:

**MONTH #1:** Planning, logistics, & preparation.

**MONTH #2:** Recruitment.

**MONTH #3:** During month #3, each cohort of 10 participants participated in four two-hour classes held weekly and facilitated by [name] with assistance from [name]. Class 1 included introductions and open-ended discussion of participants' perspectives on and experiences with MEH challenges including eliciting explanatory models of illness using a structured dialogue approach. In Class 2, [name] presented information on concepts of MEH including anxiety, depression, and social isolation, and the group explored ways that participants' own experience may align with these concepts. In Class 3 participants identified and give name to their feelings and experiences and begin to consider services they might be interested in accessing. In Class 4, [name] provided information about relevant health care and other resources, for example, school counselors, domestic violence services, Centro Sávila, The Hopkins Center, couples counseling, UNM mental health services/counseling, and church support groups.

**MONTH #4:** Over the first three weeks of month #4 of the intervention, the team conducted a preliminary analysis of class notes, observations and audio (described in the data analysis section below) to identify common themes and specific resource and service needs for each participant, and in week 4 of month #4, reconvene the groups for Class 5 to discuss findings and individual experiences with accessing resources and services since Class 4 and individual participants will develop action plans.

**MONTHS #5-7:** [name] provided individual case management to assist participants to access resources and navigate systems to achieve goals identified in their individual action plans.

**MONTH #8:** We reconvened the groups for Class 6 to engage in a follow-up discussion of outcomes and to administer the post-survey.

Mixed method data collection.

| Construct                | Instrument              | # of Items | Time point |
|--------------------------|-------------------------|------------|------------|
| Demographic Info         |                         | 18 items   | B only     |
| Depression               | PHQ-9                   | 9 items    | B&F        |
| Emotional Support        | PROMIS  | 8 items    | B&F        |
| Informational Support    | PROMIS     | 8 items    | B&F        |

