and deductive approach, coupled with the recognition that study participants and researchers 'co-construct' data, thus making it a good fit for community-engaged research. As such, analyses require inclusion of participant perspectives and meaning to be fully developed. A key aspect of this approach is its iterative nature, thus analysis will be ongoing and begin at baseline. Beginning in Month 3, notes from audio recordings were checked for accuracy and imported into NVivo 11, a qualitative data analysis software program. [name] trained [name] in qualitative coding techniques and all qualitative data will be independently coded by [name] and [name]. Analysis began with 1) text-based coding, marking recurrent themes or statements, 2) as themes emerge, [name] and [name] met to define and standardize them, agree on a structural framework and to determine how themes should be applied to coding, 3) [name] and [name] used focused coding of prominent thematic clusters and constant comparison techniques to conduct preliminary analysis of prominent themes, 4) we conducted member checking through sharing these preliminary interpretations during Class 4, using methods developed by CBPR researchers to elicit feedback and interpretation from the group, which we then incorporated into our analyses. For Aim 1, qualitative analysis of narratives from class discussion and observational notes provided insights into women's explanatory models of MEH to inform the case management and resource access phase of the intervention, the dynamics of the structured dialogue group process, how women develop and use action plans to navigate and access resources, how they explain and describe their experience in this process, and the extent to which empowering processes emerge. For Aim 2, we analyzed challenges and barriers identified by participants and identify potential strategies to promote institutional and policy changes that would positively affect MEH through advocacy. Aim 3 was assessed by looking at evaluation process data for participant perspectives on the feasibility, acceptability, value and cultural appropriateness of the intervention model.

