## Results

Intervention was acceptable and feasible. Increase in resiliency was our most robust quantitative finding. Social, emotional and informational empowerment scores improved, but not in statistically significant way. Depression scores worsened, which could reflect the effectiveness of the psychoeducation component. Qualitative results: participants' experiences in the intervention underscored the importance of recognizing cultural differences in values and meaning related to MEH: 1) Self-advocacy and self-efficacy (learning how to say "no" or set limits as Latinas) ; 2) Addressing violence (in domestic settings, in families, social violence) ; 3) Isolation and socializing (recognizing differences in U.S. v. Latin America) . Overall, the results demonstrated the importance of multilevel interventions that address mental health at multiple levels: 1) Individual:

| Research Timeline                                | Month |   |   |   |   |   |   |   |   |    |    |    |
|--|-------|---|---|---|---|---|---|---|---|----|----|----|
|  | 1     | 2 | 3 | 4 | 5 | 6 | 7 | 8 | 9 | 10 | 11 | 12 |
| Activity   |       |   |   |   |   |   |   |   |   |    |    |    |
| Planning/Logistics                               | ■     |   |   |   |   |   |   |   |   |    |    |    |
| Recruitment                                      |       | ■ |   |   |   |   |   |   |   |    |    |    |
| Cohort 1 (Classes 1-4)                           |       |   | ■ |   |   |   |   |   |   |    |    |    |
| Quantitative Baseline Interview                  |       |   |   |   |   |   |   |   |   |    |    |    |
| Cohort 2 (Classes 1-4)                           |       |   |   | ■ |   |   |   |   |   |    |    |    |
| Cohort 3 (Classes 1-4)                           |       |   |   |   | ■ |   |   |   |   |    |    |    |
| Analysis of Class Data                           |       |   |   |   | ■ | ■ |   |   |   |    |    |    |
| Class 5 – Discuss Findings, Resource Access Plan |       |   |   |   |   | ■ | ■ |   |   |    |    |    |
| Individual Case Management                       |       |   |   |   |   |   | ■ | ■ | ■ |    |    |    |
| Class 6 – Follow-up to Discuss Outcomes          |       |   |   |   |   |   |   |   | ■ |    |    |    |
| Quantitative post-interview                      |       |   |   |   |   |   |   |   |   | ■  |    |    |
| Data Analysis of Outcome Class                   |       |   |   |   |   |   |   |   |   | ■  | ■  |    |

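### Feasibility is concluded without counts or a numeric rule, and the recruitment, attrition and attendance data named in Aim 3 have no stated part in that conclusion

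*Combined protocol and SAP*

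**What the plan says.** Under Specific Aims, Aim 3 states what will be measured: "We will track recruitment, attrition, attendance at group sessions, and attendance at individual CHW navigation meetings". It adds survey and qualitative data on participants' experience, and then the hypothesis: "The intervention we pilot will be feasible, acceptable, valuable, and culturally appropriate". The Research Design paragraph fixes the planned size: "we will assess the feasibility of implementing this model with 30 participants". Intervention Implementation gives the cohort size: "each cohort of 10 participants participated in four two-hour classes held weekly". The research timeline shows three cohorts.

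The rule for judging the aim is one sentence at the end of the qualitative analysis text: "Aim 3 was assessed by looking at evaluation process data for participant perspectives on the feasibility, acceptability, value and cultural appropriateness". The quantitative analysis paragraph covers instrument scores and does not mention the tracking data.

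On what happened, the Recruitment paragraph says that the community health worker "recruited 30 participants through the Pathways Program, the Simplemente Salud Clinic and Centro Sávila". It then says that "lower numbers than anticipated joined the study from the first 3 cohort" and that delivery was therefore changed to two cohorts, one in the Fall and one in the Spring. The Conclusions add that stigma and competing demands at home and at work made early commitment hard, and that completing the survey in class was an obstacle. The Results open with: "Intervention was acceptable and feasible".

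**The concern.** The measures that would show whether women enrol, stay and attend are named and collected, but nothing says how they bear on the verdict. What does bear on it is the opinion of women who took part. That source cannot register women who never joined. The evaluation and feasibility items are also given only at follow-up, in Class 6, so women who left earlier are missing from that survey too. The source is therefore weakest on enrolment and retention, which is where the document itself reports difficulty.

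The pilot is meant as groundwork for an R21 application. Those planning that study need to know how many women can be enrolled and kept under a given schedule. An unqualified statement of feasibility, with no numbers and no schedule attached, does not tell them.

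**Working it through.** **1. The plan's own calculation.** The only design calculation is in the quantitative analysis paragraph: n = 30, d = 0.53, α = 0.05, power 0.80. For a paired t-test on change scores, two-sided (the plan does not state sidedness), the noncentrality is d√n = 0.53 × √30 = 2.90 with 29 degrees of freedom. Power is 0.801, so the figure reproduces. It concerns instrument change scores and says nothing about feasibility.

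**2. Following the Aim 3 measures through the document.**

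| Measure | Named in Aim 3 | Level that counts as feasible | Stated role in the Aim 3 verdict | Figure in Results |
|---|---|---|---|---|
| Recruitment | yes | none | none | none |
| Attrition | yes | none | none | none |
| Group attendance | yes | none | none | none |
| Navigation attendance | yes | none | none | none |
| Participant perspectives | yes | none | yes | none |

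The planned size of 30 is given in the Research Design paragraph, but reaching it is not made a criterion.

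**3. Can the shortfall be sized?** Shortfall = planned number − number who joined. Planned: 3 cohorts × 10 = 30, which agrees with the Research Design paragraph. The number who joined is not given. If recruited means joined, the shortfall is 30 − 30 = 0, which contradicts the statement that fewer joined than expected. If recruited means invited or interested, the shortfall is above zero but unknown. The size of the two revised cohorts is not stated either, and the implementation text and timeline still describe cohorts of 10 and three cohorts.

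**4. What counts would show.** Exact (Clopper-Pearson) 95% limits for x of n are the 0.025 quantile of Beta(x, n − x + 1) and the 0.975 quantile of Beta(x + 1, n − x). All counts below are assumed. The denominator of 20 supposes two cohorts of 10.

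| Assumed count | Proportion | Exact 95% CI |
|---|---|---|
| 21/30 | 70% | 51% to 85% |
| 24/30 | 80% | 61% to 92% |
| 27/30 | 90% | 73% to 98% |
| 16/20 | 80% | 56% to 94% |

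These intervals show how imprecise a pilot of this size is. They do not measure the effect of having no rule.

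**5. Was a numeric rule possible at the planned size?** Take, purely as an assumption, 60% as unacceptable and 80% as desirable. With n = 30, the smallest pass mark with one-sided error at most 0.05 is 23: P(X ≥ 23 | 0.6) = 0.044 and P(X ≥ 23 | 0.8) = 0.76. With n = 20 the mark is 17, with error 0.016 and power 0.41. A rule was workable at 30 and would be much weaker at 20.

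**The case against.** The case on the other side has real weight.

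- *The hypothesis could have failed.* Unfavourable survey or interview responses would have contradicted it. This stands: a reader might infer that nothing could have counted against feasibility, and the documents do not support that. What is missing is a numeric rule and any role for the tracked data.
- *The difficulty was disclosed.* The Recruitment paragraph and the Conclusions both report it, with reasons. This also stands, but the feasibility sentence in the Results was not narrowed to match.
- *A shortfall and a new timetable do not make an intervention infeasible.* Correct. The change described is to cohort timing, not class content, and nothing shows that a threshold would have reversed the conclusion.
- *The missed target is not established.* Correct. The same paragraph says 30 were recruited, so a missed target cannot be written as fact until the text is reconciled.
- *Feasibility is one aim of three, and no go/no-go step is described.* Correct. It should not be called the pilot's main decision.
- *Formal pass/fail rules are a matter of preference in a small mixed-methods pilot.* This is arguable, and in any case results are already written, so a bar set now would be chosen in hindsight. It does not answer the absence of counts.

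**Conclusion.** The point holds in a limited form. The measures named in Aim 3 play no stated part in judging it, no numeric rule exists, and the Results state feasibility without a count and without identifying the schedule. The document's own account of enrolment does not support so unqualified a statement.

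A reader might go further and infer that the intervention was infeasible, or that the recruitment target was missed by a known amount. Neither follows: the number who joined is not reported, and the recruitment statements conflict.

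The size of the problem therefore cannot be given from the documents. The intervals and the example rule above rest on assumed counts and assumed levels. Treating 10 per cohort as a figure set before the data is also an inference. The implementation text gives it in the past tense, but three such cohorts make up the planned 30.

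**What to change.** 1. Reconcile the Recruitment paragraph: say what recruited means, and state the numbers approached, joined, attending classes and navigation meetings, and completing Class 6 and the post-survey. Bring the implementation text and timeline into line with the two-cohort change.
2. Set the numbers who joined and started each cohort beside the plan's 30 participants and 10 per cohort, and give the proportions attending and completing with exact 95% intervals. Label the planned figures as descriptive benchmarks, not as prespecified pass/fail criteria.
3. Reword the Results so that feasibility is a descriptive finding, given separately for the original three-cohort schedule and the revised Fall/Spring schedule. If the counts fall short, do not claim feasibility for recruitment as first planned.
4. Prespecify progression thresholds for the follow-on R21 study only. Any set now for this pilot would be post hoc.

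The cost is one short table from data already tracked, and a narrower, probably less favourable, conclusion.

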## Significance

Latina MEH Disparities: New Mexico (NM) is one of five majority-minority states with 48% of the population identifying as Hispanic, a group that experiences poor health outcomes. Moreover, there is evidence of an “immigrant paradox” or “nativity effect,” wherein recent immigrants experience mental and emotional health (MEH) disorders at lower rates than native born Hispanics. However, others have cautioned that Hispanics/Latinos are not a monolithic group even within the immigrant community.

More recent research has shown that social-structural conditions negatively influence the health of the immigrant population, with significant disparities in the realm of MEH. In particular, providers in Albuquerque’s International District have identified MEH as a significant concern among Spanish-speaking Hispanic women (Latinas), especially those from the Mexican immigrant community.

Through our research and community work with this population, members of our team have found that Latinas often: 1) misrecognize MEH symptoms and are unsure how they can be addressed through existing community resources, 2) require assistance identifying and navigating systems and services, 3) lack social and emotional support, and 4) experience personal disempowerment.

The growing acceptance of **social determinants of health** frameworks that move beyond individual health in primary care settings has been a huge advance in health research for improving health outcomes, especially in relation to addressing health disparities. However, it is clear that a social determinants framework must go beyond recognizing that social determinants exist to examining the mechanisms through which social determinants operate and *how* they contribute to decision-making within structural and policy arenas. In relation to MEH, although there are evidence-based guidelines for treating individuals, these fail to address social and structural factors that contribute to disease prevalence, or to sufficiently consider culture in intervention design. We believe that given disparities in Latina MEH in NM, it is important to take a different approach. Increasing Latina MEH equity requires understanding culturally- and experientially-based explanatory models of MEH, attending to social and structural determinants, and designing non-stigmatizing, culturally-appropriate strategies for working in the community to emphasize social connectivity, empowerment, advocacy for self and others, access to resources and services, and collective engagement to identify needed policy change.

